## **Statistical Analysis**

Data management and statistical analysis were done using Statistical Package

for Social Sciences, Version 21.0 (SPSS Inc., Chicago III) for Windows. Shapiro-Wilk tests of normality were used to test normality of all quantitative variable distributions. Canine retraction in millimetres was presented as mean and standard deviation (SD). Kruskal-Wallis test was used to test the difference in the incremental rate of retraction between the two groups. Independent t-test was used to determine the statistical differences in the total distance travelled.  $P$ -value  $<0.05$  was considered statistically significant. All tests were two-sided. Concordance correlation coefficients (CCCs) were calculated to detect the intra- and inter-examiner reliability of the measurements.

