## ABSTRACT

**Objectives:** To investigate the effectiveness of AcceleDent Aura vibrating device on rate of canine retraction. **Materials and Methods:** Thirty-two patients requiring extraction of upper first premolars and canine retraction were randomly allocated with a 1:1 ratio into either no-appliance group or the AcceleDent Aura appliance group. Canine retraction was done applying 150gm of retraction force using NiTi coil springs on 16\*22 stainless steel archwires. The duration of the study was 4 months. Digital models were obtained directly after extraction of upper first premolars and at monthly intervals during canine retraction for recording the monthly as well as the total distance moved by the canine. Digitized models were superimposed on the initial model and data were statistically analyzed. Anchorage loss, rotation, tipping, torque and root condition were evaluated using cone beam computed tomography imaging. Pain was evaluated by visual analog scale. **Results:** No patients were dropped-out during this study. There was no statistically significant difference between both groups regarding the total distance travelled by the canine ( $P=0.436$ ), as well as the rate of canine retraction per month ( $P=0.17$ ). Regarding the pain level, there was no statistically significant difference between the two groups at day 0 ( $P=0.721$ ), after 24 hrs. ( $P=0.882$ ), after 72 hrs. ( $P=0.378$ ) and after 7 days ( $P=0.964$ ). **Conclusion:** AcceleDent Aura was not able to accelerate orthodontic tooth movement. Pain level couldn't be reduced by vibrational force

with an AcceleDent device during orthodontic treatment. Root condition was not affected by the vibrational forces.

**KEY WORDS:** AcceleDent; Acceleration of tooth movement; Vibrating devices; Canine retraction; Digital models

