## INTRODUCTION

Shortening of the treatment time via accelerating orthodontic tooth movement (OTM) continues to be a relentless challenge and demand in the mainstream orthodontics. To date, several modalities have been investigated to accelerate OTM through mechanical, pharmacological, surgical and physical approaches.

Vibrating devices are another example of physical acceleration of OTM. AcceleDent vibrating device (OrthoAccel Technologies, Houston, Texas) has been introduced to the market in 2009. It was intended to be used by the patients in conjunction with fixed orthodontic appliances or aligners, for 20 minutes per day. It vibrates at a frequency of 30Hz and has a force amplitude of 20 grams. The mechanism of action is hypothesized to be via enhancing bone remodelling through increased RANKL expression together with elevation in IL-1 beta levels with a result in rise of the rate of tooth movement after application of vibration in humans

and mice, respectively. The results reported in the literature concerning the efficiency of these devices in acceleration of tooth movement are controversial.

The aim of this study was to investigate the effectiveness of AcceleDent Aura vibrating device on the rate of canine retraction. The null hypothesis was that there is no difference in the rate of canine retraction between AcceleDent Aura appliance group and no appliance group. Other side effects including pain and root resorption were also considered.

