## **MATERIALS AND METHODS**

### **Trial Design**

This study was a parallel group two arm randomized controlled clinical trial with 1:1 allocation ratio that was reported following the CONSORT statement. The study was approved by the Evidence Based Center, and the Research Ethics Committee and performed at the Faculty of Dentistry, Cairo University, Egypt . All patients were acquainted with the study procedures, and signed informed consents. No changes or modifications were done to the original methodology of the research

after trial commencement. All methods were performed in accordance with the CONSORT guidelines and regulations.

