### **Sample Size Calculation**

The sample size for the current study was calculated based on the results of Kau et al. A total sample size of 52 canines was calculated to detect a large effect size ( $d=0.8$ ) with 80% power and 5% significance level. This number has been increased to a total sample size of 64 canines to count for the expected sample attrition. The outcome variable is normally distributed. The sample size was calculated using G-Power program (University of Düsseldorf, Düsseldorf, Germany).

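### Rate and total distance are compared by independent-sample tests with no stated unit of analysis, while the trial is sized in canines and 32 patients were randomised

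*Combined protocol and SAP*

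**What the plan says.** Trial Design gives the structure: "This study was a parallel group two arm randomized controlled clinical trial with 1:1 allocation ratio". The Abstract gives the number: "Thirty-two patients requiring extraction of upper first premolars and canine retraction were randomly allocated", which is 16 per arm, and reports no drop-outs. Interventions and Outcomes describes extraction and retraction on both sides, with models at T0 to T4. Each patient therefore yields two canines and four increments per canine.

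The Sample Size Calculation counts canines. "A total sample size of 52 canines was calculated to detect a large effect size" of d=0.8 with 80% power at the 5% level, and then: "This number has been increased to a total sample size of 64 canines" to allow for attrition. No correlation or design effect appears.

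The Introduction makes the rate the tested outcome: "The null hypothesis was that there is no difference in the rate of canine retraction between AcceleDent Aura appliance group and no appliance group". Under Statistical Analysis, "Kruskal-Wallis test was used to test the difference in the incremental rate of retraction between the two groups", and "Independent t-test was used to determine the statistical differences in the total distance travelled". That section does not say whether one observation is a patient, a canine or a canine-month. It mentions no averaging over sides or months, no mixed model and no cluster-robust variance. Retraction is summarised by mean and SD, with no confidence interval. The Abstract reports one P value for rate (0.17) and one for total distance (0.436), without saying how sides and months were combined.

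**The concern.** Both tests assume independent observations. Two canines in one mouth share the patient's biology, device use and operator, and four increments on one canine share more still. The tests are sound on one value per patient. They are not valid if canines or canine-months are entered as separate subjects, because the standard error is then too small when the correlation is positive.

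The only unit the document counts is the canine, so a reader has reason to suspect that the tests used it and cannot tell whether n was 32, 64 or 256. This matters most for a negative conclusion. The Abstract concludes firmly that the device did not speed tooth movement. With no interval, the reader can judge how much benefit was excluded only from the sample size, and 64 canines from 32 patients carry less information than 64 independent units.

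**Working it through.** **Inputs.** From the documents: 32 patients, 1:1; 64 canines, so 64/32 = 2 per patient; 64 × 4 = 256 increments; d=0.8, 80% power, two-sided 5%; P=0.17 and P=0.436. Assumed, because the documents give no value: between-canine correlation ρ, and for pooled increments the patient and canine shares of variance.

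**1. The stated 52.** For a two-sample t-test with d=0.8, power is 0.791 with 25 per arm and 0.807 with 26. So 2 × 26 = 52 is reproduced exactly, with each canine counted as independent. On the same basis, 32 canines per arm give 0.883.

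**2. Type I error if the canine was the unit.** The true variance of the arm difference is (1+ρ) times the one the test uses. Null simulation with 16 v 16 patients, two canines each, one normal value per canine, 40,000 trials per setting:

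| ρ | t-test, canines | Kruskal-Wallis, canines | t-test, patient means |
|---|---|---|---|
| 0 | 0.051 | 0.050 | 0.051 |
| 0.25 | 0.081 | 0.081 | 0.051 |
| 0.4 | 0.099 | 0.097 | 0.051 |
| 0.6 | 0.120 | 0.116 | 0.047 |

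**3. Type I error if all 256 increments were pooled, with no month trend.** With patient share p and canine share c, the design effect is 1 + 3(p+c) + 4p. For p/c of 0.1/0.1, 0.3/0.1 and 0.5/0.1 this is 2.0, 3.4 and 4.8. The approximation 2{1 − Φ(1.96/√DE)} gives 0.17, 0.29 and 0.37. Simulated Kruskal-Wallis (4,000 trials each) gives 0.165, 0.285 and 0.359.

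**4. Information and power at patient level.** Effective canines = 64/(1+ρ). If d=0.8 is on the single-canine SD, the effect on patient means is 0.8/√((1+ρ)/2), tested with 30 df:

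| ρ | Effective canines | d on patient means | Power, 16 v 16 |
|---|---|---|---|
| 0.2 | 53.3 | 1.033 | 0.807 |
| 0.4 | 45.7 | 0.956 | 0.744 |
| 0.6 | 40.0 | 0.894 | 0.687 |

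Power equals 0.80 at ρ of about 0.22. This fits the attrition margin: 64/52 = 1.23, so the unused allowance absorbs a design effect of about that size and no more. If d=0.8 already refers to patient means, power with 16 v 16 is 0.59 whatever ρ is.

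**5. Reported P values, if each came from 64 canines with one value per canine.**
- Total distance: P=0.436 on 62 df is t=0.784. Dividing by √(1+ρ) and referring to 30 df gives 0.48, 0.51 and 0.54 at ρ = 0.2, 0.4 and 0.6.
- Rate: of 60,000 simulated trials per ρ, those with canine-level Kruskal-Wallis P of 0.165 to 0.175 (537, 546 and 540 trials) had median patient-mean P of 0.228, 0.258 and 0.274. At most 0.6% fell below 0.05.

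**6. Interval width.** Patient-level over canine-level: √(1+ρ) × 2.042/1.999, which is 1.12 at ρ=0.2 and 1.29 at ρ=0.6.

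**The case against.** The strongest reply is that the investigators may have averaged to one value per patient, which would make both tests valid. The documents do not exclude this, so a reader who infers that the analysis was wrong goes too far. What stands is that the unit is unstated and the only unit counted is the canine.

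A second reply is that the results were null, so clustering cannot matter. It is true that no false positive was claimed. But a reader might infer that the results stay non-significant under any correction, and that is not shown. It holds for one value per canine. For a Kruskal-Wallis test on all 256 increments, a strong month trend common to both arms adds variation that masks the arm comparison. In simulated settings with an assumed trend SD of 1.5 times the within-month SD, where the pooled test had become conservative (type I error 0.8% or less), 22% to 84% of trials with pooled P of 0.16 to 0.18 had patient-mean P below 0.05. The documents report no such trend, and not every setting with one behaves this way, but it rules out the general claim.

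Third, a reader might infer that total distance rests on only 18 patients, because the CBCT measurements section lists it and 18 scan pairs are reported. The Abstract and Interventions and Outcomes both assign total distance to the digital models, so this reading is poorly supported. The count of 18 scan pairs against 32 patients is a separate point.

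Fourth, the power figures depend on which SD defines d=0.8. The document does not say, so both readings are given.

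**Conclusion.** The concern holds and should be fixed. The sample size treats 64 canines as independent, and the analysis names independent-sample tests without saying what one observation is. That a canine-level or increment-level analysis was actually run is likely from the text, not established.

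If the canine was the unit, t-test type I error is about 8% to 12% for ρ of 0.25 to 0.6, and 64 canines are worth about 53 to 40 independent ones for ρ of 0.2 to 0.6. If all increments were pooled with no month trend, the error is about 0.16 to 0.37 for the variance shares tried. Whatever analysis was run, the 80% power target is met at patient level only for ρ up to about 0.22 with d on the single-canine SD, and is missed (0.59) with d on patient means.

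All of this rests on assumed correlations. Nothing here suggests that the device works or that the reported direction is wrong. The damage is to precision: the document does not define how firmly a benefit has been excluded, and probably overstates it.

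**What to change.** - State under Statistical Analysis that the patient is the unit of analysis.
- Compare total distance from the digital models, as the mean of the two canines per patient, 16 v 16 by t-test. Report the arm difference with a 95% CI.
- Analyse the monthly rate by a linear mixed model with arm, month and arm-by-month, and random effects for patient and for canine within patient. A canine effect alone would still treat a patient's two canines as independent.
- Do not add a separate test on the mean of the four increments. All models are superimposed on T0, so if displacement is taken along one axis the increments sum to the total and their mean is total distance divided by 4. That test would largely repeat the first; the new information is in the monthly course.
- Restate the power in the Sample Size Calculation at patient level over a range of assumed correlations, and say which SD d=0.8 refers to.

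The cost is a short re-analysis of data already held and a paragraph of text. The interval will probably be wider than a canine-level one, by a factor of 1.12 to 1.29 for ρ of 0.2 to 0.6, which is the price of stating the precision correctly.
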